5.2 Exclusion Criteria

Subjects are excluded from the study if any of the following criteria apply:

Disease Related

238 Symptomatic central nervous system (CNS) metastases:

- Subjects with treated brain metastases are eligible provided the following criteria are met:

- Subjects with untreated brain metastases that are asymptomatic and do not require corticosteroids, nor local therapy per investigators standard of practice are allowed

202 Diagnosis or evidence of leptomeningeal disease.

203 Prior history of immune checkpoint inhibitors resulting in:

- Any severe or life-threatening immune-mediated adverse event

- History of immune-mediated encephalitis or other immune-mediated CNS event (any grade)
- Grade ≥ 2 immune-mediated recurrent pneumonitis
- Infusion-related reactions leading to permanent discontinuation of immunotherapy agent

Exception: Subjects with a history of immune checkpoint inhibitor-induced endocrinopathy which is clinically stable on replacement therapy.

Other Medical Conditions

204 Active autoimmune disease that has required systemic treatment (except replacement therapy) within the past 2 years or any other diseases requiring immunosuppressive therapy while on study.

205 History of solid organ transplantation.

206 History of other malignancy within the past 2 years, with the following exceptions:

- low-risk malignancy treated with curative intent and with no known active disease present for ≥ 1 year before enrollment and believed to be at low risk for recurrence per investigator discretion.
- adequately treated non-melanoma skin cancer or lentigo maligna without evidence of disease.
- adequately treated cervical carcinoma in situ without evidence of disease.
- adequately treated breast ductal carcinoma in situ without evidence of disease.
- prostatic intraepithelial neoplasia without evidence of prostate cancer.
- adequately treated urothelial papillary noninvasive carcinoma or carcinoma in situ.

207 Myocardial infarction and/or symptomatic congestive heart failure (New York Heart Association > class II) within 12 months prior to first dose of study treatment (Section 11.9).

208 History of arterial thrombosis (eg, stroke or transient ischemic attack) within 12 months prior to first dose of study treatment.

239 Presence/history of viral infection:
Human immunodeficiency virus (HIV) infection

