Neurologic Events					
4		Immediately stop any ongoing infusion	Follow institutional guidelines for management and administer corticosteroids per local practice; Consider diagnostic workup for alternate diagnosis. ^f Transfer to ICU Reference dose of corticosteroids for Grade 4 ICANS. ^f Methylprednisolone 1000 mg/day in divided doses IV for 3 days followed by taper as clinically indicated. Consider additional therapies per guidelines.	Permanently discontinue	Permanently discontinue
Seizure	Reference Section 11.11.2 for grading and management guidelines	Delay tarlatamab until the event improves to grade $\leq 1^g$	Administration of corticosteroids and anti-seizure medication is permissible based on investigator judgment and local practice.	Do not resume tarlatamab until 7 days after the last seizure and after therapeutic levels of anti-seizure medication are likely to have been achieved.	If a second seizure occurs after resuming tarlatamab

Abbreviations and footnotes defined on last page of table.

Table 6-2. Tarlatamab Dose Modification Guidelines for Adverse Events

Grade	Description of Severity ^a	Interruption/Delay Specific Management	Restart guidance	Permanent Discontinuation
1	Cytokine Release Syndrome (see Section 11.11.1 for additional guidance and grading scale details)	
Administer:
 
• Symptomatic treatment (eg, paracetamol/acetaminophen) for fever• Consider a single dose of dexamethasone (or equivalent) ranging from 4 mg to 10 mg.• Monitor:
• CRS symptoms including temperature, blood pressure, and pulse oximetry• Fluid status, maintain IVF as needed• Consider Chest X-ray and obtaining appropriate cultures to rule out infection 
For subjects with rapid onset (< 4 hours from start of infusion), extensive co-morbidities or poor PS, strong suggestion to manage per grade 3 CRS guidance below and local institutional guidelines.
	
No additional guidance
	
No additional guidance

Abbreviations and footnotes defined on last page of table.

Table 6-2. Tariquetamab Dose Modification Guidelines for Adverse Events

Grade	Description of Severity ^a	Interruption/Delay	Specific Management	Restart guidance	Permanent Discontinuation
Cytokine Release Syndrome continued (see Section 11.11.1 for additional guidance and grading scale details)					

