4 (cont)			
If tocilizumab is not available, siltuximab (an anti-IL-6 monoclonal antibody) may be used in the management of CRS, following the criteria outlined in this table. The recommended dose of siltuximab is 11 mg/kg administered over 1 hour as an IV infusion, consistent with the prescribing information for the treatment of multicentric Castleman's disease (Sylvant Prescribing Information), and the CARTOX Working Group Guidelines for CRS management (Neelapu et al, 2018). Siltuximab may be repeated if needed, in the event that CRS recurs after a subsequent infusion of tarlatamab. Siltuximab may not be repeated in an individual subject who develops anaphylaxis to siltuximab, or gastrointestinal perforation after siltuximab. 
Monitor:
 
CRS symptoms including temperature, blood pressure, and pulse oximetryFluid status, maintain IVF as neededConsider chest X-ray and obtaining appropriate cultures to rule out infectionIf refractory hypotension (after 2 fluid boluses), consider ECHO 
Admit to intensive care unit for close clinical and vital sign monitoring per institutional guidelines.
		

Abbreviations and footnotes defined on last page of table.

Table 6-2. Tarlatamab Dose Modification Guidelines for Adverse Events

Grade	Interruption/Delay	Specific Management	Restart guidance	Permanent Discontinuation
Tumor Lysis Syndrome (TLS) – Grading according to Common Terminology Criteria for Adverse Events (CTCAE v5.0) (see Section 11.11.3)				
Present	Immediate interruption/delay until event has improved to grade ≤ 1	
TLS should be managed according to the local SOC and institutional guidelines.
 
• Resume only if successfully managed and improvement to \leq grade 1 in ≤ 14 days• Consult with Amgen medical monitor.• In case of infusion interruption, continue treatment with next schedule infusion, do not resume prior infusion or administer delayed infusion.• Monitoring: per Monitoring Guidance for first tarlatamab administration (Section 6.1.1)	
If subject missed more than 2 consecutive doses of tarlatamab
 
OR
 
In case of repeat TLS event, or life-threatening TLS, permanently discontinue tarlatamab.
	

Abbreviations and footnotes defined on last page of table.

Table 6-2. Tarlatamab Dose Modification Guidelines for Adverse Events

Grade	Interruption/Delay	Specific Management	Restart guidance	Permanent Discontinuation

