8.4.6 Adverse Events and Serious Adverse Events

The method of recording, evaluating, and assessing causality of adverse events, and serious adverse events and the procedures for completing and transmitting serious adverse event reports are provided in [Section 11.4 with the following exceptions:](#)

CRS and ICANS will be graded according to American Society for Transplantation and Cellular Therapy (Lee et al, 2019) as described in [Table 6-2](#) and [Section 11.11](#).

8.4.6.1 Time Period and Frequency for Collecting and Reporting Safety Event Information**8.4.6.1.1 Adverse Events**

The adverse event grading scale to be used for this study will be the CTCAE v5.0 and is described in Section 11.4.

The investigator is responsible for ensuring that all adverse events observed by the investigator or reported by the subject that occur after the first dose of investigational product(s) or noninvestigational product(s)/auxiliary medicinal product(s) through the SFU visit or **60** days after the last dose of investigational product(s) or non-investigational product(s)/auxiliary medicinal product(s), whichever is later, are reported using the Events CRF.

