11.11.2 Specific Guidance for Immune-effector Cell-associated Neurologic Syndrome

For this trial, ICANS will be using the criteria referenced in the publication by Lee et al, 2019. While the grading system has been developed in large part from chimeric antigen receptor T cells (CAR-T) therapies, symptoms of ICANS may be shared among immune effector cell-associated therapies such as bispecific T cell engager (BiTE) molecules. Although there may be a wide range of symptoms associated with ICANS, subjects may have a stereotypic course of a specific set of symptoms. The earliest manifestations of ICANS are tremor, dysgraphia, mild difficulty with expressive speech (especially in naming objects), impaired attention, apraxia, and mild lethargy.

Immune effector cell-associated neurologic syndrome grade is determined by the most severe event (eg, depressed level of consciousness, seizure, motor findings, raised intracranial pressure [ICP]/cerebral edema) not attributable to any other cause. Refer to the immune effector cell-associated encephalopathy (ICE) score below for grading of ICANS.

Immune Effector Cell-associated Encephalopathy (ICE) Assessment Tool

The ICE tool was designed to provide objectivity for the grading of multiple overlapping encephalopathy terms. The tool includes an element for assessing the receptive aphasia seen in these subjects. The total score that after assessing the following questions will be used as an input in the determination of the ICANS grade.

- Orientation: Orientation to year, month, city, hospital: 4 points
- Naming: ability to name 3 objects (eg, point to clock, pen, button): 3 points
- Following commands: ability to follow simple commands (eg, "Show me 2 fingers" or "Close your eyes and stick out your tongue"): 1 point

- Writing: ability to write a standard sentence (eg, “Our national bird is the bald eagle”): 1 point
- Attention: ability to count backwards from 100 by 10: 1 point

ICE Scoring

- 7-9, grade 1
- 3-6, grade 2
- 0-2, grade 3
- 0 due to subject unarousable and unable to perform ICE
- Assessment, grade 4

Table 11-7. ASBMT Immune Effector Cell-associated Neurotoxicity Syndrome (ICANS) Consensus Grading for Adults

Neurotoxicity Domain ^a	Grade 1	Grade 2	Grade 3	Grade 4
ICE score ^b	7-9	3-6	0-2	0 (subject is unarousable and unable to perform ICE)

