Depression level of consciousness ^c	Awakens spontaneously	Awakens to voice	Awakens only to tactile stimulus	Subject is unarousable or requires vigorous or repetitive tactile stimuli to arouse. Stupor or coma
Seizure	N/A	N/A	Any clinical seizure focal or generalized that resolves rapidly or nonconvulsive seizures on EEG that resolve with intervention	Life-threatening prolonged seizure (> 5 min); or repetitive clinical or electrical seizures without return to baseline in between
Motor findings ^d	N/A	N/A	N/A	Deep focal motor weakness such as hemiparesis or paraparesis
Elevated ICP/cerebral edema	N/A	N/A	Focal/local edema on neuroimaging ^e	Diffuse cerebral edema on neuroimaging; Decerebrate or decorticate posturing; or Cranial nerve VI palsy; or Papilledema; or Cushing's triad

ASBMT = American Society for Blood and Marrow Transplantation; CTCAE = Common Terminology Criteria for Adverse Events; EEG = electroencephalogram; ICANS = immune effector cell-associated neurologic syndrome; ICE = immune effector cell-associated encephalopathy; ICP = intracranial pressure; N/A = not applicable.

^a Other signs and symptoms such as headache, tremor, myoclonus, asterixis, and hallucinations may occur and could be attributable to immune effector-cell engaging therapies. Although they are not included in this grading scale, careful attention and directed therapy may be warranted.

^b A subject with an ICE score of 0 may be classified as grade 3 ICANS if awake with global aphasia, but a subject with an ICE score of 0 may be classified as grade 4 ICANS if unarousable.

^c Depressed level of consciousness should be attributable to no other cause (eg, no sedating medication).

^d Tremors and myoclonus associated with immune effector cell therapies may be graded according to CTCAE v5.0, but they do not influence ICANS grading.

^e Intracranial haemorrhage with or without associated edema is not considered a neurotoxicity feature and is excluded from ICANS grading. It may be graded according to CTCAE v5.0.

Source: Lee et al, 2019

Assessment and Supportive Care Recommendations (all grades)

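### Table 6-2 does not say that a grade 4 seizure follows the grade 4 row, so the ungraded Seizure row can be read as allowing tarlatamab to be resumed

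*Protocol*

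**What the plan says.** Protocol Section 6.2.2.1, Table 6-2, has a block for neurologic events with rows for grades 1 to 4 and a further row labelled only as seizure.

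- **Grade 4 row.** Stop any running infusion, transfer to intensive care and give high-dose methylprednisolone. Both the restart cell and the permanent-discontinuation cell read "Permanently discontinue". No exception is made for seizures.
- **Seizure row.** Delay until the event is at grade 1 or below, which footnote g ties to CTCAE 5.0. Corticosteroids and anti-seizure drugs are optional. The restart cell reads "Do not resume tarlatamab until 7 days after the last seizure and after therapeutic levels of anti-seizure medication are likely to have been achieved". The permanent-discontinuation cell lists one trigger: "If a second seizure occurs after resuming tarlatamab".

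For grading, the Seizure row refers to Section 11.11.2. Table 11-7 there grades immune effector cell-associated neurotoxicity syndrome (ICANS) and defines a grade 4 seizure as "Life-threatening prolonged seizure (> 5 min); or repetitive clinical or electrical seizures without return to baseline in between". The same section sets the ICANS grade by the most severe finding "not attributable to any other cause", with seizure among its examples.

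For adverse events in general, Section 8.4.6.1.1 says "The adverse event grading scale to be used for this study will be the CTCAE v5.0"; Section 8.4.6 makes CRS and ICANS exceptions.

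**The concern.** One event, a grade 4 seizure attributed to ICANS, meets two rows of the same table. One row ends treatment. The other describes the conditions for going back on treatment and does not mention severity. The protocol does not say which row governs, or that the Seizure row is limited to lower grades.

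What is at stake is subject safety and consistent dosing across about 240 planned sites. A site following the grade 4 row would never give tarlatamab again. A site that reasons that the row naming the event is the specific rule could give it again after a life-threatening seizure. The Seizure row also has no check that would catch this. Restart after grade 3 CRS or after tumor lysis syndrome calls for contact with the sponsor's medical monitor, and restart after a seizure does not.

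**Working it through.** No arithmetic applies. The check compares the two rows for a single event, then looks for any text that settles precedence.

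**Step 1. Does a grade 4 seizure fall under both rows?** Yes. The Seizure row has no grade limit, and Table 11-7 defines a grade 4 seizure. Because the most severe finding sets the ICANS grade, such a seizure attributed to ICANS is a grade 4 neurologic event.

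**Step 2. What does each row lead to for a first grade 4 seizure?**

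| | Grade 4 row | Seizure row read alone |
|---|---|---|
| Running infusion | Stop | Not addressed |
| Restart | None | Possible once three conditions hold: CTCAE grade 1 or below, 7 days since the last seizure, anti-seizure drug levels probably adequate |
| Permanent stop | At the first event | Only at a second seizure after resuming |

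**Step 3. Can both rows be met at once?** Yes. The restart cell of the Seizure row is worded as a prohibition with a minimum wait. A site that stops for good breaches neither row.

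**Step 4. Does anything state that the grade 4 row prevails?** I looked in four places.

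- The lead-in to Section 6.2.2.1 lets the investigator delay or stop for toxicity. It allows an earlier stop but does not close the restart path.
- The footnotes to Table 6-2 give no order of rows. Footnote g only names a grading scale.
- Section 11.11.2 sends the reader back to Table 6-2 for management.
- The Amendment 1 summary says grade 4 neurologic events are to lead to permanent discontinuation. It does not mention seizures, and a later amendment summary reports that the neurologic and seizure guidance was revised again. It hints at intent but does not settle the current text.

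**Step 5. Is grade 3 affected in the same way?** No. The grade 3 row asks for at least 72 hours before resuming and the Seizure row for 7 days. Waiting 7 days meets both, and the permanent-stop triggers of the two rows can be applied together.

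**Step 6. What about seizures with another cause?** Table 11-7 covers ICANS only. Exclusion 238 in Section 5.2 admits "Subjects with untreated brain metastases that are asymptomatic and do not require corticosteroids", as well as some subjects with treated brain metastases, so seizures from other causes are possible. Those would be graded by CTCAE 5.0, whose seizure grades the protocol does not reproduce. The documents do not settle whether a grade 4 seizure of that kind must be a permanent stop.

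**The case against.** The strongest reply is that the rows are cumulative. They share one heading, the grade 4 instruction is unqualified, and the Seizure row only forbids early resumption. The Seizure row also cannot stand alone for a grade 4 event: it does not mention the running infusion or intensive care, and it gives no steroid dose. Its grading reference leads to Table 11-7 and so back to the grade 4 row. On this view, re-dosing would mean ignoring an explicit instruction one row above.

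Much of this stands. A reader might infer that the two rows give opposite orders, or that the protocol authorises restart after a grade 4 seizure. The documents do not support either inference, since one action satisfies both rows and no sentence grants permission to restart at grade 4.

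What does not fall away is the permanent-discontinuation cell of the Seizure row. That is where a grade 4 stop for seizures would be looked for, and it names only a recurrence. Reading the row that names the event as the specific rule is an ordinary way to use such a table, and the cumulative reading, though plausible, is nowhere stated.

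A reader might also point to the tumor lysis row, which says "In case of repeat TLS event, or life-threatening TLS, permanently discontinue tarlatamab", as proof that a severity stop was left out of the Seizure row. That comparison is weak. Tumor lysis has no separate grade rows, so its severity stop had to be written there; seizures already have a grade 4 row above them.

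**Conclusion.** The point holds as an unstated precedence, not as a contradiction. For a grade 4 seizure as defined in Table 11-7, the intended action is probably permanent discontinuation, but the Seizure row leaves a readable path to re-dosing from 7 days after the last seizure, and no text closes it.

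The difference for an affected subject is large: never treated again, or treated again once three conditions are met. How many subjects this could concern cannot be estimated, because the documents give no seizure frequency. No endpoint, analysis, error rate or sample size depends on it.

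The conclusion rests on two assumptions: that the table cells were read correctly from the PDF, where the restart and permanent-discontinuation cells of both rows appear intact, and that the seizure is attributed to ICANS. It does not extend to grade 3 seizures, where the rows are already compatible. Nor does it show that grade 4 seizures with a clear non-ICANS cause must end treatment; that is a clinical decision the documents leave open. The change is worth making because the event is life-threatening and the edit is very small.

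**What to change.** Add one sentence to both the restart cell and the permanent-discontinuation cell of the Seizure row: *A grade 4 seizure per Table 11-7 follows the grade 4 row: permanently discontinue.* Leave the row otherwise unchanged, so that it continues to govern lower-grade seizures.

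The sponsor's clinical team should decide, and then state, whether the same stop applies to a grade 4 seizure with a clear cause other than ICANS, such as brain metastases.

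A line saying that the grade row and the Seizure row both apply would help readers at grade 3, but it is optional.

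The cost is one sentence in two cells and a communication to sites. Data collection and the statistical analysis do not change.

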6.2.3 Hepatotoxicity Stopping and Rechallenge Rules

Refer to Section [11.7](#) for details regarding drug-induced liver injury guidelines, as specified in the Guidance for Industry Drug-Induced Liver Injury: Premarketing Clinical Evaluation, July 2009.

6.3 Preparation/Handling/Storage/Accountability

Guidance and information on drug accountability for the investigational product and non-investigational products(s)/auxiliary medicinal product(s) will be provided to the site.

6.4 Method of Treatment Assignment

Subjects will be randomized in a 1:1 allocation ratio, to receive tarlatamab or SOC therapy (lurbinectedin or topotecan in US, Canada, Australia, Singapore, Korea; amrubicin in Japan; or topotecan in all countries except Japan), respectively, in an open-label manner. For subjects randomized to the SOC arm in US, Canada, Australia, Singapore, and Korea, lurbinectedin or topotecan may be selected for treatment based on investigator discretion.

The stratification factors are:

- Prior anti-PD-(L)1 exposure (yes vs no)
- Chemotherapy-free interval (\geq 180 days, < 180 to \geq 90 days, or < 90 days)
- Presence (previous or current) of brain metastases (yes or no)
- Standard of care (topotecan/amrubicin vs lurbinectedin)

The randomization will be performed by IRT, and the randomization number will be provided to the site via IRT. The randomization date is to be documented in the subject's medical record and on the Subject Enrollment CRF (via IRT).

6.5 Blinding

To maintain trial integrity in this open-label study, post-baseline data analyses of primary and key secondary endpoints will not be produced or reviewed by the study team prior to interim/primary analysis snapshot analysis.

6.6 Treatment Compliance

When subjects are dosed at the site, they will receive study treatment directly from the investigator or designee, under medical supervision. The date and time of each dose administered in the clinic will be recorded in the source documents and recorded on the CRF.

When subjects self-administer oral topotecan at home, compliance with the treatment will be assessed through a web-based diary and documented in the source documents and CRF. The web-based diary **should** be completed daily with the response 'Yes' (if oral topotecan is taken) or 'No' (if oral topotecan has not been taken, in the event of dose interruption due to adverse event, etc.).

6.7 Treatment of Overdose

The effects of overdose of tarlatamab are not known. For overdose information on SOC chemotherapy, please refer to the regional prescribing information or institutional guidelines (if not addressed in prescribing information) for recommended treatment for overdose.

The administered tarlatamab dose may be up to 10% lower or higher than specified in the protocol. A dose of up to 10% higher than the intended dose may not require specific intervention.

In any case of overdose, consultation with the Amgen medical monitor is required for prompt reporting of clinically apparent or laboratory adverse events possibly related to overdosage. Consultation with the Amgen medical monitor is also required even if there are no adverse events, in order to discuss further management of the subject. If the overdose results in clinically apparent or symptomatic adverse events, the subject should be followed carefully until all signs of toxicity are resolved or returned to baseline and the adverse event(s) should be recorded/reported (**refer to Section 11.4, Appendix 4**).

A dose of \geq 10% higher than the intended tarlatamab dose will be considered clinically important and classified as a serious adverse event under the criterion of "other medically important serious event".

